17.0 References

PROSPECTIVE EVALUATION OF CYBERKNIFE STEREOTACTIC RADIOSURGERY FOR LOW AND INTERMEDIATE RISK PROSTATE CANCER: EMULATING HDR BRACHYTHERAPY DOSIMETRY

SCHEMA

PATIENT POPULATION (see section 4.0 for complete eligibility)

Histologically-confirmed, adenocarcinoma of the prostate

Clinical Stage T1b - T2b, NX-0, MX-0

One of the following combinations:

- Gleason score 2-6 and PSA 20
- Gleason score 7 and PSA 10

ECOG Performance Status 0-1

No prior prostate radiation or other definitive therapy

Required sample size: 253

ELIGIBILITY CHECKLIST

(Y)	Is there histologically proven prostate adenocarcinoma, biopsy within one year of enrollment?
(2-6)	What is the Gleason Score?
(T1b - T2b)	What is the clinical T-stage? (AJCC 6 th Edition)
(Y)	Is the patient clinical Nx or N0, and Mx or M0?
(0-20)	What is the patient's PSA?
(L, I)	Does the patient fall into one of these risk groups (AJCC 6 th Edition): - Low: CS T1b-T2a, Gleason 2-6, PSA 10 - Intermediate: CS T2b, Gleason 2-6, PSA 10, or CS T1b-T2a, and Gleason 2-6, PSA 20 ng/ml, or Gleason 7, PSA 10 ng/ml
(0-1)	What is the ECOG performance status?
(N)	Has the patient undergone prostatectomy or cryotherapy of the prostate?
(N)	Has the patient had radiotherapy to the prostate or lower pelvis?
(N)	Is there implanted hardware near the planning target volume that would prohibit appropriate treatment planning or treatment delivery in the investigator's opinion?
(N)	Has the patient had chemotherapy for a malignancy in the last 5 years?
(N)	Has the patient had an invasive malignancy (other than this prostate cancer, or basal or squamous skin cancers) in the last 5 years?
(N)	Has the patient's androgen function been ablated during the past 2 months?

1. BACKGROUND

- 1.1. During the prostate-specific antigen era, an ever-increasing percentage of men with prostatic adenocarcinoma have presented with clinically localized, intermediate Gleason grade, potentially curable disease. Conventional treatment options for these patients include laparoscopic or open radical prostatectomy, external beam radiation therapy, permanent source interstitial brachytherapy, and high dose rate (HDR) remote after loading brachytherapy, either as monotherapy, or in combination with external beam radiotherapy.¹
- 1.2. Although each of the treatment options is potentially curative in selected patients, each treatment option also has drawbacks. The post-operative recovery period may be substantial following radical prostatectomy; the period of urologic symptoms may be protracted and occasionally severe following permanent source brachytherapy; the scheduling duration is substantial for external beam radiotherapy and the discomfort of indwelling transperineal catheters is significant for HDR brachytherapy patients. Additionally, all local treatments carry a risk of negative long-term quality of life consequences, and occasionally, serious complications.
- 1.3. The use of hypofractionated CyberKnife stereotactic therapeutic radiation as a modality of treatment for early-stage prostate cancer has also been described. In contradistinction to traditional external beam radiotherapy, this method entails a therapeutic radiation process that uses a more precise targeting methodology, allowing a more focal treatment margin around the prostate. This more effectively limits the volume of adjacent tissue receiving high dose radiation, which in turn allows the delivery of a much shorter series of treatments, employing a much larger dose of radiation per treatment. When so applied, the radiation becomes tissue ablative within the high dose zone, and as such, may be described as a form of radiosurgery.
- 1.4. Although very limited experience has been gained to date, the radiosurgical approach for prostate cancer carries with it a number of potential advantages, including the possibility of lower morbidity due to the very small treatment margins, more rapid recovery from side effects due to the lack of a surgical resection or implanted radioactivity, convenience of a one week treatment course, and lack of transperineal HDR catheters with their attendant pain and hospital admission requirement.
- 1.5. The main technical problem that prevents the application of radiosurgery for prostate cancer is that the prostate may move substantially, both between fractions (interfraction motion) and during the treatment itself (intrafraction motion), even if rigid body immobilization is applied, due to the effect of organ motion.^{3,4} This prostate motion effect necessarily leads to the application of a larger radiotherapy planning target volume to compensate, effectively rendering radiosurgery impossible by traditional radiotherapy or radiosurgical systems.
- 1.6. The CyberKnife® is a unique noninvasive radiosurgical system, capable of treating any part of the body from any of approximately 1600 different targeting angles, creating a highly conformal three-dimensional radiosurgical treatment volume, guided by orthogonal X-ray-based targeting feedback, and delivering radiation by a highly collimated, robotically controlled linear accelerator. The CyberKnife® system targets implanted fiducial markers with sub-millimeter initial set-up accuracy, and continuously updates the planning target volume by obtaining multiple intrafractional orthogonal X-ray-images, producing an automated robotic adjustment after each X-ray feedback step, resulting in a real-time target volume tracking process that maintains millimeter accuracy throughout the

radiosurgical treatment.⁵ Thus, the CyberKnife® device allows a reproducible method of radiosurgical prostate treatment.

- 1.7. There are also radiobiological data that suggest hypofractionated radiosurgical treatment may be advantageous for prostate cancer, as contemporary data suggest the α/β ratio for prostate cancer tissue may be as low as 1.5Gy.⁶ These values of α/β are comparable to, if not lower, than late-responding normal tissues.⁶ This means that in addition to causing effective cancer cellular ablation and tissue sparing due to of its physics attributes, a course of hypofractionated CyberKnife® prostate radiosurgery may also create a favorable therapeutic ratio by virtue of the radiobiologic sensitivity of prostate cancer itself to hypofractionation, effectively resulting in radiobiologic tumor dose escalation.^{6,7}
- 1.8. From a dosimetry standpoint, CyberKnife® radiosurgery appears capable of producing a dose distribution comparable to that created by prostate HDR brachytherapy treatment, without the invasive transperineal catheters. As such, the CyberKnife® prostate radiosurgery dose fractionation schedule prescribed in this study is based upon prior published prostate HDR brachytherapy monotherapy experience, which suggests efficacy and safety, with a median follow-up duration of 35 months. The radiosurgery volume in this study will be made to resemble prostate HDR brachytherapy therapeutic volume as closely as possible, with similar dose limitation objectives to adjacent tissues, including the rectum, bladder and urethra.
- 1.9. Because of the narrow treatment margin, and sharp fall off of radiation dose beyond the treatment margin, it is only appropriate to include patients with a high likelihood of localized disease for CyberKnife® monotherapy. These patients are reasonably identified by examination of the Partin Tables⁹, which predict the probability of pathologic disease extension beyond the prostate, and also by examination of the long term results of permanent source brachytherapy literature^{10,11}, as permanent source brachytherapy produces a therapeutic margin of similar magnitude to the therapeutic margin provided by CyberKnife treatment as described in this protocol. The long-term brachytherapy literature describes biochemical disease free survival rates exceeding 80% for favorable prognosis and selected intermediate prognosis patients as described in this protocol.^{10,11}
- 1.10. The inclusion criteria and planning target volume (PTV) margin specifications in this protocol are designed such that the risk of disease extension beyond the PTV will be less than 5% for "favorable prognosis" patients (Gleason score ≤6 and PSA ≤10ng/ml) and less than 10% for "intermediate prognosis" patients (Gleason score 7 or PSA 10.1 − 20ng/ml). Patients will be stratified according to their prognostic grouping.
- 1.11. Planning target volume (PTV) margins will be based upon the risk and predicted magnitude of extracapsular extension, as most recently reported by Chao, KK, et al, detailed in sections 6.1.2 − 6.1.4 of this protocol document. Briefly, for classic "favorable" prognosis patients (PSA≤10ng/ml, T-stage <= T2a and Gleason score ≤ 6), a radial margin of 2mm will be added around the prostate to create the planning target volume. The radial margin will be increased to 5 mm posterolaterally for the "intermediate prognosis" and positive perineural invasion cases, to account for their increased risk and potential radial distance of extracapsular extension from the prostate, which typically occurs along the neurovascular bundle. Proximal seminal vesicle coverage will be added for intermediate risk patients or those with prostate base involvement as detailed in section 6.1.1 of this document. In

all cases, where the outer surface of the rectum abuts the posterior surface of the prostate, the PTV margin in that area will be reduced to zero.

- 1.12. As most patients with low and intermediate risk prostate cancers survive at least 10 years after intervention, the morbidity associated with therapy for early stage prostate cancer is a crucial factor of patient outcome. Although traditional, physician-reported toxicity data are a useful component for evaluating treatment-related morbidity, it has been shown that patient-report data (collected via standardized questionnaires) are more sensitive than physician reports to the full severity and broad range of therapy effects on patient Health-Related Quality of Life (HRQOL), particularly among men with prostate cancer.¹³
- 1.13. The feasibility of CyberKnife for treating localized prostate cancer was first described by King at Stanford University. Their phase I protocol delivered 36.25Gy in 5 fractions of 7.25Gy. In a recent report of acute and 18-month late toxicity in 26 "low-risk" patients, no patient experienced grade 3 or 4 acute or late toxicity, and only one patient experienced a grade 2 late morbidity (urethral stricture). Toxicity was less than that reported in MD Anderson's external beam dose escalation trial. Mean PSA 18 months after treatment was 0.22ng/m¹⁴.
- 1.14. Another potential benefit of CyberKnife radiosurgery relative to HDR brachytherapy is better preservation of potency, even if the radiation distribution is essentially identical between these modalities. This is so because needle trauma has been identified as a potentially significant contributory factor to erectile dysfunction with brachytherapy, including HDR-based monotherapy technique, presumably due to direct physical injury to the neurovascular bundle and/or bulb of the penis, particularly when greater than 13 needle insertions are performed.¹⁵ By comparison, CyberKnife radiosurgery is noninvasive, and so removes this particular erectile dysfunction risk factor.
- 1.15. To confirm our hypothesis that CyberKnife radiosurgery may be made to resemble a "noninvasive HDR dosimetry delivery system," in addition to simply creating equivalent dosimetry, it is necessary to show clinical equivalence both in terms of efficacy and toxicity.

Table 1. 5-Year bDFS Outcomes for HDR-Monotherapy for Prostate Cancer

HDR Details	Institution	# pts	Medianf/u yrs	Phoenix	ASTRO
6-7.25 Gy x 6	CA Endocurie ¹⁸	117	3.3		97%
9.5 Gy x 4	Beaumont ¹⁹	95	4.2		98%
7.5 Gy x 6	Texas Tech ²⁰	145	5		90%
6.5 Gy x 6	Gamma West – Fav. (SLC) ²¹	209	1.2	96%*	99%*
	Gamma West – Int. 21	119	1.2	89%*	89%*
6 Gy x 8-9	Osaka (Japan) ²²	111	2.25		70%†
	Totals	796	2.4		90%

^{*3} year result; Projecting constant failure rate in this series to 5 years yields 98% and 82% ASTROdefinition PSA DFS for favorable and intermediate risk cases, respectively. †Predominantly unfavorable prognosis cases in this series; 5 year local control is 97%.

Based on the data provided in the reports summarized above, and adding a PSA DFS degradation factor to the Gamma West series to compensate for their short median follow-up, the average calculated 5 year HDR monotherapy ASTRO-based PSA DFS is 98% for favorable prognosis, 82% for intermediate prognosis and 59% for unfavorable prognosis cases. There are too few Phoenix-based PSA DFS results to project a meaningful Phoenix-based HDR monotherapy PSA DFS efficacy result.

It is anticipated that the case mix in this study will be approximately 70% low risk/ 30% intermediate prognosis cases, leading to a predicted CyberKnife monotherapy 94% 5 year PSA DFS rate, with a potential range of 82% (0% favorable or low risk prognosis cases accrued) to 98% (100% favorable cases accrued). If the protocol case mix deviates from these percentages, then the protocol DFS rate required to successfully test the primary efficacy hypothesis detailed in Section 2.0 may need to be adjusted accordingly.

Table 2. Toxicity review for HDR-Monotherapy for Prostate Cancer

				>= Gd 3 toxicity	•	
HDR Details	Institution	# pts	Median f/u	Total (%)	GI (%)	GU (%)
6-7.25Gy x 6	CA Endocurie ¹⁸	117	3.3	3	0	3
9.5Gy x 4	Beaumont ¹⁹	95	4.2	8	0	8
7.5Gy x 6	Texas Tech ²⁰	145	5	5-8*	1	4 – 7*
6.5Gy x 6	Gamma West (SLC) ²¹	328	1.2	1	0	1
6Gy x 8-9	Osaka (Japan) ²²	111	2.25	7	1	6
	Totals	796	2.4	6	0 -1	5

^{*3%} acute and 4% chronic grade 3 GU toxicity – It is unclear to what degree acute and chronic grade 3 GU toxicity populations overlap in this study.

Due to short median follow-up, the incidence of >= grade 3 late toxicity is likely underestimated. We project that the incidence of late toxicity will increase by approximately 50% when all data reach 5 years maturity, yielding a projected cumulative 5 year HDR monotherapy grade 3 toxicity incidence of 9% (7-8% GU; 1-2% GI). In this study, biochemical disease-free survival (ASTRO and Phoenix definition), freedom from local recurrence, freedom from distant relapse, clinical disease-free survival, disease-specific survival and overall survival will be recorded. The incidence of grade 3 or higher toxicity and the effect of CyberKnife® radiosurgery on bladder, bowel, and sexual function will be followed and monitored using standardized, patient self-administered questionnaires and compared with results published in peer-reviewed literature for other prostate cancer therapeutic modalities. 17

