We chose N large enough to test the null hypothesis against the alternative hypothesis with power equal to 80% at the one-sided 5% significance level.

Let Z_u denote the upper u-th percentile of the standard normal distribution. Hence $Z_{.05} = 1.645$ corresponding to the one-sided 5% level of significance and $Z_{.20} = 0.84$ corresponds to 80% power. Then the sample size is determined by Formula 1:

$$N = \frac{\left[z_{\beta}\sqrt{\pi_{1}(1-\pi_{1})} + z_{\alpha}\sqrt{\pi_{0}(1-\pi_{0})}\right]^{2}}{\left[\pi_{1} - \pi_{0}\right]^{2}}, \text{ where}$$

 π_1 is the expected proportion of CyberKnife treated patients bDFS at 5 years if the alternative hypothesis is true; the bDFS rate is then expected to equal or exceed 0.94. For purposes of sample size estimation, we require 80% power if $\pi_1 \geq 0.945$. π_0 is the expected lower limit of the 95% confidence interval for π and is set equal to 0.90. Then N= 232. Allowing 8% sample size degradation for lost to follow-up, the sample size must be increased to 232/.92 = 253 subjects.

Primary Safety Objective

The primary safety objective is to establish with 95% confidence that the percentage of CyberKnife treated patients experiencing \geq Grade 3 toxicity is not more than 5% higher than the approximately 9% 5-year rate extrapolated from Table 2, Section 1.15.

With N=232 CyberKnife treated subjects, if the observed \geq Grade 3 toxicity rate equals 9%, then with 95% confidence the "true" rate \leq 12.6%. Since the difference between 12.6% and 9% is less than 5%, the sample size of 232 subjects is more than large enough to meet the primary safety objective.

11.3.1 ACCRUAL RATE: the initial three months while institutions are obtaining IRB approval, therefore we do not expect to meet the targeted monthly accrual rate until after the first three months. The estimated accrual rate is 2 patients per study site per month. Expectations of 5 treating study sites assumes an accrual period of approximately 29 months total.

11.4STATISTICAL METHODS

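### The plan's own inputs predict a 5-year rate of 93.2% to 93.5%, not the 94% or more stated in Section 11.3 nor the 94.5% used for sizing, so power at the predicted rate is about 49% to 63%, not 80%

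*Combined protocol and SAP*

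**What the plan says.** The text after Table 1 in Section 1.15 states that "the average calculated 5 year HDR monotherapy ASTRO-based PSA DFS is 98% for favorable prognosis, 82% for intermediate prognosis". The Table 1 footnote shows the same two values as a constant-failure-rate projection to 5 years of 3-year rates of 99% and 89%. The plan then anticipates "approximately 70% low risk/ 30% intermediate prognosis cases, leading to a predicted CyberKnife monotherapy 94% 5 year PSA DFS rate". It gives a range from 82% with no favorable cases to 98% with only favorable cases, and adds that the rate required for success may need adjusting if the case mix differs.

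Section 11.3 tests a null rate of 90% with "power equal to 80% at the one-sided 5% significance level". Of the alternative it says "the bDFS rate is then expected to equal or exceed 0.94", but it takes the 80% power at a rate of 0.945. This gives N = 232, raised to 253 for 8% loss to follow-up. Section 11.4.1 declares efficacy if the lower limit L of the one-sided 95% interval is not below 90%.

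**The concern.** The end points of the range in Section 1.15 show that the overall prediction is a linear blend of the two risk-group rates. A 70/30 blend of the printed rates is below 94%. Section 11.3 nevertheless treats 0.94 as a floor for the expected rate, and then sizes the trial half a point higher, at a value that no stated case mix produces.

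The gap is small in percentage points but large for power, because the prediction lies only 3 to 4 points above the 90% null. At stake is how a missed criterion would be read. A reader who takes the 80% at face value would see a miss as evidence that CyberKnife falls short of HDR, although exact equality with the plan's HDR figures would produce a miss quite often. The pairing of 70/30 with 94% is also the reference point from which Section 1.15 would adjust the required rate, so an inflated reference would carry into that adjustment.

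**Working it through.** **Inputs.** Section 1.15: 98% favorable, 82% intermediate, about 70/30, predicted 94%. Table 1: 3-year ASTRO-definition rates of 99% and 89%. Section 11.3: null 0.90, sizing rate 0.945, one-sided 5%, 80% power, 8% loss. Section 11.4.1: success if L is at least 0.90.

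**1. The plan's sample size reproduces.** Formula 1 in Section 11.3, with z = 1.645 and 0.84:

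N = [0.84 x sqrt(0.945 x 0.055) + 1.645 x sqrt(0.90 x 0.10)]² / (0.045)² = 231.7, so 232.

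232 / 0.92 = 252.2, so 253. Both stated figures are right for a rate of 0.945.

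**2. The blended prediction.**

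- Printed whole percents: 0.70 x 98 + 0.30 x 82 = 93.2%.
- Constant-rate (exponential) projection, unrounded: 0.99^(5/3) = 98.34% and 0.89^(5/3) = 82.35%; 0.70 x 98.34 + 0.30 x 82.35 = 93.54%.
- Linear projection, which also prints as 98 and 82: 1 - 0.01 x 5/3 = 98.33% and 1 - 0.11 x 5/3 = 81.67%; the blend is 93.33%.

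All three are below 94.0%. With the printed rates, exactly 94.0% needs (94 - 82)/16 = 75% favorable cases, and 94.5% needs (94.5 - 82)/16 = 78.1%.

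**3. The success threshold.** L from Section 11.4.1:

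- n = 232: 216 disease-free gives L = 0.8984 (fail); 217 gives L = 0.9035 (pass). The threshold is 217/232 = 93.5%.
- n = 253: 235 gives L = 0.8975 (fail); 236 gives L = 0.9021 (pass). The threshold is 236/253 = 93.3%.

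The observed proportion needed for success therefore sits almost on the plan's own prediction.

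**4. Exact power.** This is the binomial probability of at least 217 of 232, or at least 236 of 253:

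| True 5-year rate | n = 232 | n = 253 |
|---|---|---|
| 94.5% (sizing value) | 79% | 84% |
| 94.0% (printed prediction) | 68% | 74% |
| 93.54% (unrounded blend) | 57% | 63% |
| 93.2% (printed inputs) | 49% | 54% |

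Inverting Formula 1 gives nearly the same at n = 232: 80.0%, 68.7%, 57.4% and 49.0%.

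**5. Chance of a miss at the plan's prediction.** From 1 - 0.63 = 37% to 1 - 0.49 = 51%.

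**The case against.** The strongest reply is that 94% is not an error at all. The plan derives 98% and 82% from a projection; carried unrounded, the blend is 93.54%, which prints as 94%. The mix is only approximate, and even with the printed rates a 72/28 mix gives 93.52%, which also rounds to 94%. This stands as far as it goes: the documents do not prove an arithmetic slip, and 93.2% cannot be called the one true prediction. It does not rescue Section 11.3. A value of 93.5% rounded up cannot serve as a floor of 0.94, and it does not reach 0.945.

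A second reply is that the 94% does not drive the design, because N comes from 0.945. This is correct, and N, alpha, the 90% threshold and the success rule are all unaffected. It also means that part of the shortfall (79% to 68% with 232) comes from sizing at 94.5% rather than 94.0%. But it confirms that the claimed power belongs to a rate the plan does not itself predict.

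Third, Section 11.2 counts 260 subjects. If all 260 were evaluable, which is an assumption, the rule needs 242 disease-free and exact power is 59% at 93.2% and 68% at 93.54%. That is better, but still below 80%.

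A reader might also infer from the Table 1 footnote that 98% and 82% come from one series with 1.2 years' median follow-up, and so are not an average of the reports. The documents do not settle this. The text says the rates rest on all the reports, and it gives 59% for unfavorable cases, a figure absent from Table 1, so other risk-group data may have been used.

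**Conclusion.** The concern holds in this form: the expectation in Section 11.3 exceeds what the plan's inputs give on every reading examined. Exact power at the plan's own prediction is about 49% to 57% with 232 evaluable and 54% to 63% with 253. Even if 94.0% is accepted, power is 68% to 74%. If CyberKnife exactly equalled the plan's HDR figures, the efficacy criterion would be missed roughly 4 to 5 times in 10.

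It would go too far to say that a miss is the most likely result. A miss is favored only at 93.2% with 232 evaluable, and then by 51 to 49; in the other three combinations of blend and sample size, success is the more likely outcome.

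The conclusion assumes a 70/30 mix, a blended rate between 93.2% and 93.54%, independent binomial outcomes, and the Section 11.4.1 rule applied to the evaluable patients. Severity is moderate: a planning statement needs correcting, but the test and the sample size calculation stand as computed.

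**What to change.** - **Section 1.15, text after Table 1:** give the blended prediction as 93.2%, or as 93.5% with a statement that unrounded projections were used. This also corrects the reference point for any case-mix adjustment of the required rate.
- **Section 11.3:** replace the expectation of 0.94 or more with the same value. Beside the 80% power at 94.5%, state the power at the predicted rate: about 49% (at 93.2%) or 57% (at 93.5%) with 232 evaluable, and 54% or 63% with 253.

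Leave the description of where 98% and 82% come from as it is, since the documents do not show it to be wrong. No patients are added and the 90% criterion does not change. The cost is wording in two sections, and a stated expectation and power that are less favorable than now.
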